### 6.3 Follow-up:

A follow-up appointment will be arranged about 1-2 weeks after the next expected menstruation. Information collected at the follow-up visit will include side effects and vaginal bleeding/spotting marked by the subject on her diary card; time of onset, duration and amount of menstrual bleeding and any further acts of intercourse and the type of contraception used (refer to Appendix 1).

If normal menstrual bleeding has not occurred by that time, a pregnancy test will be carried out, and a positive result denotes treatment failure and the woman will be counselled accordingly. If the woman opts for continuing with pregnancy, she will be referred for antenatal care. An additional research follow-up will be arranged post-delivery to record any antenatal, postnatal and neonatal complications. If the woman opts for terminating the pregnancy, she will be referred to the appropriate services.

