## 9. Statistics

### 9.1 Statistical tests:

- The efficacy-evaluable population will include all women who are enrolled into the study and can be contacted for a follow-up where the outcome data are collected.
- Cases with missing data in a certain parameter will not be analysed for that specific parameter; no data imputation will be instituted.
- The percentage of pregnancies prevented will be compared between groups by  $\chi^2$  test.
- Logistic regression model using Firth's bias reduction method will be applied to compare the pregnancy rates between groups. Confidence intervals for regression coefficients will be computed by penalised profile likelihood. This is a statistical method recommended for rare events (Puhr R, Heinze G, Nold M, Lusa L, Geroldinger A. Firth's logistic regression with rare events: accurate effect estimates and predictions? Stat Med 2017; 36(14): 2302-2317).
- The rate of occurrence of menstrual changes will be compared between groups using  $\chi^2$  test (for nominal categorical variables) and  $\chi^2$  test for trend (for ordinal categorical variables).

- The rate of occurrence of adverse events will be compared between groups by Fisher's exact test as some of the cells may contain an expected frequency of less than 5.
- Continuous variables between the two groups will be compared by Student's t-test.
- Statistical analyses will be performed using SPSS version 28 (IBM Corporation, New York, USA), MedCalc version 20 (MedCalc Software Limited, Ostend, Belgium) and R package "logistf" Version 4.1.2 (<http://www.r-project.org>).
- P-value <0.05 will be considered as statistically significant.

Two subgroup analyses will be performed. The first subgroup analysis will stratify participants into pre-ovulatory versus post-ovulatory at the time of EC based on blood results of serum oestradiol, progesterone and luteinising hormone level on the day of EC (Li et al, 2016). The second subgroup analysis will stratify participants within versus over the body weight limits recommended for the usual dose of LNG-EC (by the cut-off of body mass index at 26 kg/m^2 and that of body weight at 70 kg).

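### Section 9.1, as written, drops non-pregnant women still without menses at the visit from the cycle-length comparison in days, shrinking any true lengthening (secondary outcome)

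*Combined protocol and SAP*

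**What the plan says.** All references are to the combined protocol and SAP.

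- **Outcome.** Section 7 lists change in the length of the current cycle, in days, as a secondary outcome.
- **Follow-up (section 6.3).** "A follow-up appointment will be arranged about 1-2 weeks after the next expected menstruation". The visit collects, among other items, "time of onset, duration and amount of menstrual bleeding". "If normal menstrual bleeding has not occurred by that time, a pregnancy test will be carried out". The text gives a next step only for a positive result, and the one extra visit is after delivery. No later contact is described for a woman who has no menses and a negative test.
- **Missing data (section 9.1).** "Cases with missing data in a certain parameter will not be analysed for that specific parameter; no data imputation will be instituted".
- **Tests (section 9.1).** "Continuous variables between the two groups will be compared by Student's t-test". For categories, "The rate of occurrence of menstrual changes will be compared between groups using" a chi-square test, or chi-square for trend if ordinal. No test is named for cycle length, so I read the comparison in days as the t-test. No censoring rule is given.
- **Efficacy population (section 9.1).** Enrolled women who "can be contacted for a follow-up where the outcome data are collected". Section 9.2 expects about 10% to default. No sensitivity analysis is described for them.

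**The concern.** A woman who tests negative and has not bled by the visit has no cycle length in days. Under the rule in section 9.1 she leaves that comparison, and the reason is that her cycle is long. The missingness therefore depends on the outcome itself, and the analysed sample is cut off at about 7 to 14 days after expected menses. If piroxicam lengthens cycles, the women who show it most are removed, more of them from the piroxicam arm, and the difference in days shrinks towards zero.

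Section 2 makes a delay plausible and no more. It reports that COX-2 inhibitors may delay follicle rupture, but most of those studies gave other drugs for 5 days or longer. The one single-dose study with LNG (n=41) showed a non-significant trend.

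**Working it through.** **1. The plan's own figure.** For 52% v 62%, two-sided 5%, 80% power, pooled variance:
n = [1.96 × √(2 × 0.57 × 0.43) + 0.842 × √(0.52 × 0.48 + 0.62 × 0.38)]² / 0.10² = 384 per arm, as section 9.2 states. Then 384 / 0.9 = 427 per arm, 854 in total, against 860 stated. The sample size is not in dispute.

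**2. Women available.** 860 × 0.9 / 2 = 387 followed per arm. At the 2.15% LNG pregnancy rate in section 2, 387 × 0.0215 = 8.3 pregnancies, which leaves about 379 non-pregnant women per arm.

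**3. Truncation formula.** Let the deviation of menses from the expected date be a mixture of normals with weights w, means μ and SDs σ. With a visit on day V and a = (V − μ)/σ:
- share kept: P = Σ w Φ(a)
- mean among those kept: Σ w [μ Φ(a) − σ φ(a)] / P

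For visits spread evenly over +7 to +14, numerator and denominator are each averaged over V first.

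Worked case: uniform 2-day shift, SD 6, V = 10.5.
- Control: a = 1.75; mean = −6 × 0.0863 / 0.9599 = −0.54; 4.0% dropped.
- Treated: a = 8.5/6 = 1.417; mean = 2 − 6 × 0.1463 / 0.9217 = 1.05; 7.8% dropped.
- Observed difference: 1.05 + 0.54 = 1.59 days of a true 2.

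**4. Results, visits even over +7 to +14.** The documents give no SD or delay distribution, so every scenario is an assumption. In the delayed-minority rows the other women have mean 0 and SD 4.

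| Assumed lengthening | True diff. (days) | Observed | Loss | Dropped, control v treated |
|---|---|---|---|---|
| Uniform 1 day, SD 3 | 1.00 | 0.98 | 2% | 0.1% v 0.4% |
| Uniform 2 days, SD 4 | 2.00 | 1.85 | 8% | 0.9% v 2.9% |
| 10% v 20% delayed, mean 7 (SD 3) | 0.70 | 0.56 | 20% | 2.5% v 4.1% (10 v 16 women) |
| 10% v 20% delayed, mean 9 (SD 4) | 0.90 | 0.50 | 45% | 4.5% v 8.1% (17 v 31) |
| 5% v 15% delayed, mean 12 (SD 4) | 1.20 | 0.36 | 70% | 4.0% v 10.2% (15 v 39) |

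Visit timing matters. With every visit at +14, the three delayed-minority rows lose 2%, 16% and 39%, and a uniform 1-2 day shift with SD 3-4 loses under 1%.

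**5. Power (simulation, 379 per arm; 4,000 trials, 1,000 for Tobit).**
- Mean delay 7: the t-test falls from about 55% to 41%.
- Mean delay 9: it falls from about 68% to 33%.
- Censored at the visit, on the scale of deviation from expected menses: Tobit 54% and 67% (estimates 0.69 and 0.87 days); log-rank 64% and 78%.
- With equal arms there is no bias, and type I error is 4.7-5.6% for these two censored methods.

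**6. Women lost to follow-up.** 860 × 0.10 / 2 = 43 per arm. Expected pregnancies without EC: 430 × 0.0215 / 0.48 = 19.3 per arm, so one unseen pregnancy moves that arm's fraction prevented by 1 / 19.3 = 5.2 points. At the design rates the 43 carry about 43 × 0.0215 = 0.9 pregnancies in the placebo arm and 0.9 × 0.38 / 0.48 = 0.7 in the piroxicam arm.

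**The case against.** **Later dates may be captured.** The premise rests partly on silence. Appendix 1, the data collection sheet, is not in the text reviewed. Section 4 allows 2 months after recruitment for follow-up to finish, section 6.2 gives each woman a bleeding diary, and section 9.1 speaks of contact, not of a single clinic visit. This stands as a condition on the finding. None of it states that a menses date after the visit is recorded.

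**The chi-square comparison.** A reader might infer that it also loses these women. The documents do not impose that. No menses at the visit is an observed category, not a missing one, and section 9.1 does not say how it is counted. Any power loss would also depend on a cut-off for lengthening that the plan does not define. The gap is that the rule is unstated.

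**How long the delay is.** The visit time is approximate and the trigger is absence of normal bleeding, so a delay of more than 7 days is not certain for each such woman. Lengthened would usually still be right.

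**Size.** The loss can be negligible (small SD, late visits) or large (a minority with long delays). The scenarios above are illustrations, not bounds.

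**Lost women.** A reader might infer that leaving them out biases the efficacy result. That needs loss which is related to outcome and also differs by arm. Blinding makes this less likely, and the expected counts are small.

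**Conclusion.** The point holds for the comparison in days. If section 9.1 is followed as written, and Appendix 1 does not record later menses dates, women are excluded because their cycle is long, and any true lengthening is biased towards no difference. The bias arises only if the arms differ in lengthening; with equal distributions the exclusions balance.

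The size cannot be fixed from the documents. Under the assumptions shown, the loss runs from about 2% or less (small uniform shift, or a 7-day delay with all visits at +14), through 20-45% (10% v 20% delayed by 7 to 9 days), to about 70% (5% v 15% delayed by 12 days).

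A reader might infer that the primary outcome suffers too. It does not by this mechanism, because women without menses have a pregnancy test at the visit. This concerns one secondary outcome and is worth considering, with medium confidence. The missing sensitivity analysis for lost women is minor.

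**What to change.** 1. **Categories.** State in section 9.1 that a non-pregnant woman without menses at the visit counts as lengthened in the chi-square comparison. This is observation, so it does not conflict with the ban on imputation.
2. **Days.** Analyse the deviation of menses from the expected date, with these women censored at last contact, by a Tobit-type model (result in days) or log-rank. Report the t-test as supplementary and handle pregnancies separately. Do not use time from EC: in the simulations log-rank power on that scale fell to 30-43% (mean delay 7) and 47-60% (mean delay 9).
3. **Where possible,** record the later menses date by phone within the six-week availability in section 5.1. This reaches 42 − (28 − 14) = 28 days past expected menses in a 28-day cycle with EC on day 14, but only 42 − (42 − 10) = 10 days in a 42-day cycle with EC on day 10. The censoring rule is therefore still needed. If Appendix 1 already collects the date, say so in section 9.1.
4. **Optional and minor.** Add one tipping-point table over all randomised women, with 0 to 3 pregnancies among the lost in each arm, showing the fraction prevented and the Firth result.

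Cost: SAP wording, one censored model, and the optional table; no new visits. Calls would number about 25 to 48 in the 7- and 9-day scenarios. Tobit assumes normal errors and understates very long delays (1.29 v 1.80 days at a mean delay of 18 days), and log-rank does not give a difference in days.

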UPA, another selective progesterone receptor modulator, has more recently been introduced as an oral EC. Two randomized controlled trials showed that UPA was as effective as LNG for EC within 72 hours of UPSI (Creinin et al, 2006; Glasier et al, 2010). When the results of the two RCTs were combined in a meta-analysis, UPA has significantly lower failure rate compared to LNG [1.36% (22/1617) vs 2.15% (35/1625),  $p=0.046$ ] (Glasier et al, 2010). The effectiveness of UPA as EC is maintained up to 120 hours after UPSI, which is currently the licensed indication of UPA. In contrast to LNG which has a limited administration period preceding the onset of the LH surge for it to be effective, it was demonstrated that a single dose of 30 mg UPA administered up till the time immediately before the LH peak could still significantly interfere with follicular rupture (Brache et al, 2010). It was initially postulated in some studies that UPA might also have some concurrent inhibitory effect on embryo implantation based on changes in some molecular and histological parameters induced by UPA, but this was not supported by subsequent in-vitro co-culture experiments. One study in Hong Kong also did not support a significant clinical effect of UPA as EC when administered post-ovulation (Li et al, 2016). Therefore, the journey in search of further improvement in the efficacy of oral EC methods, particularly one with effective post-ovulatory action, still continues.

Prostaglandins are “local hormones” that take part in a number of reproductive processes including ovulation (Duffy, 2015), fertilisation (Sugimoto et al, 2015), tubal function (Wanggren et al, 2006; Wanggren et al, 2008) and embryo implantation (Salleh, 2014). Hence, it is postulated that an inhibitor of the cyclo-oxygenase (COX) enzyme, the key enzyme involved in prostaglandin production, may potentially confer a “contraceptive”

effect and may act synergistically with LNG for EC, particularly to target at the post-ovulatory events in addition.

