## 7. Study outcomes

### Primary outcome measure:

- Fraction of pregnancies prevented (%)  
[(expected pregnancies – observed pregnancies] / expected pregnancies]  
The number of expected pregnancies will be determined by the Trussell's model (Trussell J et al, Contraception 2003; 67:259-265)

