### Secondary outcome measures:

- Pregnancy rate (%)
- Change in length (shortening / lengthening) of current cycle (days)
- Adverse effects

The data collection sheet is included in Appendix 1. All the clinical data are part of the usual consultations for EC provision.

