## 9.2 Sample size estimation:

In a previous study on using LNG for EC within 72 hours of UPSI (Glasier et al, 2010), the fraction of prevented pregnancies was 51.9% based on the Trussell's model. With the assumption that the fraction of prevented pregnancies in the placebo group is around 52%, and the fraction of prevented pregnancies in the treatment group should be at least 10% higher than that in the placebo group for it to be clinically meaningful, a minimum of 384 subjects in each group will be required to demonstrate superiority of the proposed treatment with a power of 80% and type I error of 0.05. Assuming that around 10% of the subjects may default follow-up, we plan to recruit a total of 860 subjects.

No interim analysis is planned as it is anticipated that co-administration of oral piroxicam with LNG will not adversely reduce its EC efficacy.

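### The primary chi-square treats the prevented fraction, 1 − observed/expected, as a proportion of yes/no outcomes; its variance is too small and the 5% error rate is not held

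*Combined protocol and SAP*

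**What the plan says.** Section 7 defines the primary outcome as the ratio "expected pregnancies – observed pregnancies] / expected pregnancies" and adds that "The number of expected pregnancies will be determined by the Trussell's model". Section 9.1 then says "The percentage of pregnancies prevented will be compared between groups by" a chi-square test, at a 0.05 significance level. It does not say what the table contains, what the denominator is, or how the variance of an observed-to-expected ratio is obtained.

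Section 9.2 starts from an earlier levonorgestrel study in which "the fraction of prevented pregnancies was 51.9% based on the Trussell's model", takes 52% for placebo and 10 points more for piroxicam, and concludes that "a minimum of 384 subjects in each group will be required to demonstrate superiority of the proposed treatment with a power of 80"%.

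Section 9.1 also states "Logistic regression model using Firth's bias reduction method will be applied to compare the pregnancy rates between groups". Section 7 lists "Pregnancy rate" among the secondary outcomes.

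**The concern.** A chi-square comparison of two percentages needs units that are each counted as yes or no. Here the only random count is the number of observed pregnancies. The expected number is a sum of modelled risks, nobody can be classed as having had a pregnancy prevented, and the fraction turns negative when observed exceeds expected. If the fraction is entered as though it were a binomial proportion, the standard error is wrong whichever denominator is chosen.

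This is the test on which the superiority claim rests. If its false-positive rate is far above 5%, a significant result says little about piroxicam. Because the error is in the variance, it can also produce a significant result in favour of placebo.

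**Working it through.** **The plan's own figure.** For 52% vs 62%, two-sided 5%, 80% power, pooled variance and no continuity correction:

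n = [1.96·√(2·0.57·0.43) + 0.8416·√(0.52·0.48 + 0.62·0.38)]² / 0.10² = (1.3723 + 0.5862)² / 0.01 = 383.6, so 384 women per arm.

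The stated size is reproduced, and it treats each woman as one binomial observation of the prevented fraction. One-sided testing would give 303, so two-sided 5% is used below.

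**Input not in the plan.** The expected pregnancy rate r is not given. Section 2 reports failure rates of "1.36% (22/1617) vs 2.15% (35/1625"), the second being levonorgestrel. Dividing by one minus the prevented fraction in section 9.2 gives r = (35/1625)/(1 − 0.519) = 4.48%. This is an assumption: it joins a pooled two-trial rate to a fraction attributed to one study. A range of 3% to 8% is therefore shown. At 4.48%, the expected number per arm is E = 384 × 0.0448 = 17.2.

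**Variance in one arm** (PF = prevented fraction, observed count approximately Poisson, E fixed):

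- True: (1 − PF)/E
- Chi-square, expected pregnancies as denominator: PF(1 − PF)/E, which is PF = 0.52 of the true value at any r
- Chi-square, women as denominator: PF(1 − PF)/N, which is PF·r = 0.52 × 0.0448 = 0.023 of the true value

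**Standard error of the difference**, both arms at 52%, E = 17.2, N = 384:

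- True: √(2·0.48/17.2) = 0.236
- Expected pregnancies: √(2·0.52·0.48/17.2) = 0.170
- Women: √(2·0.52·0.48/384) = 0.036

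**False-positive rate by formula**, 2[1 − Φ(1.96·√variance ratio)]: √0.52 = 0.721 gives 15.8%; √0.0233 = 0.153 gives 76%.

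**False-positive rate with discrete counts**, 384 per arm, both arms at 52%. The first figure in each cell is exact enumeration with equal fixed E and Poisson counts. The second is simulation of 400,000 trials with E varying between arms (assumption: 30% of women fertile, conception probability r/0.3).

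| r | Women | Expected pregnancies | Expected, continuity-corrected | Conditional exact | Conditional mid-p |
|---|---|---|---|---|---|
| 3% | 87.9 / 81.1% | 17.8 / 16.2% | 9.7 / 8.6% | 2.3 / 2.0% | 4.2 / 3.8% |
| 4.48% | 71.3 / 76.2% | 17.6 / 15.2% | 11.1 / 9.1% | 2.8 / 2.2% | 4.6 / 3.7% |
| 6% | 74.8 / 72.1% | 16.8 / 14.5% | 11.2 / 9.3% | 3.0 / 2.3% | 4.5 / 3.6% |
| 8% | 64.8 / 67.4% | 16.7 / 13.6% | 11.8 / 9.1% | 3.1 / 2.2% | 4.5 / 3.4% |

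With women as denominator a continuity correction changes the rate by about 1 point. That column is not smooth in r because the counts are small. Negative fractions were set to 0; in the enumeration, observed exceeds expected in at least one arm in only 0.4% of trials at 4.48% (2.3% at 3%), so this does not drive the result. Under a true 52% vs 62% at 4.48%, the women-denominator test is significant in the wrong direction in 20% to 22% of trials.

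**Example.** 8 placebo and 6 piroxicam pregnancies, 17.2 expected in each arm: PF = 1 − 8/17.2 = 53.5% and 1 − 6/17.2 = 65.1%. The p-value is 0.001 with women as denominator, 0.49 with expected pregnancies, 0.79 by the exact conditional test and 0.61 by mid-p. Two pregnancies separate the arms.

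**The case against.** The strongest objection is that section 9.1 does not say how the table is built, and a chi-square need not go wrong. Testing the split of observed pregnancies between arms against the split of expected ones has the right null hypothesis and rejects in 4.4% to 5.3% of null trials under the fixed-E enumeration. A table with observed and expected as separate cells rejects in only about 1% to 2%. The plan describes neither. Neither compares the percentage as a proportion, as the text says, and neither fits the sample-size basis. What stands is that the first of these would be an acceptable repair if written down.

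The choice of women as denominator is also an inference from 384, since a sample-size formula shows how a trial was sized and not how it will be analysed. This is fair, and it is why the two readings are kept separate. The milder one still fails, at roughly twice the nominal rate with a continuity correction and three times without.

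Third, randomisation balances expected risk on average, so the Firth analysis addresses nearly the same null hypothesis and would be reported beside the primary result. That limits the harm but does not make the primary p-value valid.

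Finally, the 4.48% rate and the 30% fertile share are assumptions. They affect the size of the error, mainly with women as denominator, but not its direction.

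**Conclusion.** The concern holds, and the test must be changed before the primary p-value can be used. Entered as a proportion, the prevented fraction gets a variance that is 0.52 of the true value with expected pregnancies as denominator and about 0.02 with women. With expected pregnancies the variance ratio needs no outside figure; with women the size of the inflation depends on the assumed expected rate. The reading that matches the plan's own sample size is the worse one. Uncertainty in the model's cycle-day risks was not added; it would tend to widen the true variance further.

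**What to change.** Replace the primary chi-square in section 9.1 by a conditional binomial test, choosing exact or mid-p in advance. Given the total number of pregnancies, test the piroxicam count against probability E_T/(E_T + E_P), where E_T and E_P are the expected pregnancies in the piroxicam and placebo arms, summed over the same evaluable women as the observed ones. The exact form is conservative (2% to 3%); mid-p is nearer nominal (3% to 5%). Poisson regression with a log(expected) offset targets the same ratio but is not numerically identical (Wald p = 0.59 in the example).

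Report (1 − PF_T)/(1 − PF_P) with its interval (example: 6/8 = 0.75, exact 95% CI 0.21 to 2.46). Report each arm's prevented fraction with an exact Poisson interval that may go below zero (example: 53.5%, 8.4% to 79.9%; 65.1%, 24.1% to 87.2%). Keep the Firth analysis as supporting.

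The change is a few lines of text, runs in the R software already named and needs no new data. The real cost is in section 9.2, where the 80% power must be restated. At 384 per arm, 52% vs 62% has about 4% power (exact) or 6% to 7% (mid-p) at 4.48%; over 3% to 8% it is 3% to 6% exact and 5% to 8% mid-p. On the log rate ratio, the size for 80% power is N = (1.96 + 0.8416)²·(1/0.48 + 1/0.38)/(r·[ln(0.38/0.48)]²). This is roughly 15,100 women per arm at 4.48%, 22,600 at 3% and 8,500 at 8%. Even if the sample size cannot change, the plan should say what the trial can and cannot show.

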### 4. Study design:

This will be a randomised placebo-controlled double-blind clinical trial. A dedicated research nurse will help coordinate subject recruitment, study administration and follow-up of subjects. Subjects who give written consent to participate in this study shall be randomised to either the piroxicam arm (Treatment group) or placebo arm (Placebo group) in 1:1 ratio according to a computer-generated randomisation list in blocks of 10 in sealed envelopes which are prepared by an independent person. The medication will be prepacked by an authorised third party not directly involved in this study. The subjects, clinicians and research staff will be blinded to the group assignment. The codes for the treatment groups will only be revealed to the investigators after completion of the whole study and statistical analyses. It is anticipated that subject recruitment shall take 20 months; follow-up of the subjects will be completed in 2 months further, and a summary of preliminary results will be available by 24 months.

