### 5. Subject selection and exclusion

#### 5.1 Inclusion criteria

Women attending the Family Planning Association of Hong Kong for oral EC will be recruited if they fulfil the following criteria:

- (a) healthy women aged 18 years or above;
- (b) requesting emergency contraception within 72 h of a single act of unprotected intercourse in the current menstrual cycle;
- (c) having menstrual cycles between 24 and 42 days
- (d) willing to abstain from further acts of unprotected intercourse and;
- (e) available for follow-up over the next 6 weeks.

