#### 5.2 Exclusion criteria

- (a) post-abortion or postpartum and period have not yet returned,
- (b) being on the following drugs currently: anticoagulants, cyclosporine, tacrolimus, corticosteroids, lithium, serotonin reuptake inhibitors (SSRIs), quinolones
- (c) having unprotected intercourse in this cycle more than 72 hours or more than once before attending the clinic,
- (d) being found pregnant at the time of presentation,
- (e) breastfeeding,
- (f) having been sterilized (or partner having been sterilized) or having intrauterine contraceptive device in-situ,
- (g) uncertain about the date of the last menstrual period,
- (h) having used hormonal contraceptive (including EC pill) in the current or past one cycle, or NSAID in the recent one week,

- (i) having history of asthma, urticaria or other allergic reactions to piroxicam, aspirin or other NSAIDs,
- (j) having history of ischaemic heart disease, heart failure, hypertension or cerebrovascular disease
- (k) having history of peptic ulcer disease and/or gastrointestinal bleeding

The proposed start date of this study is 1 August 2018, and it is anticipated that study recruitment will last for two years.

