## 6. Treatment of subjects

### 6.1 Baseline assessment:

- The subject will be assessed and counselled for the use of EC by the clinic nurse or doctor as routine. Suitable subjects will be enrolled for the study after informed consent.
- A menstrual history will be taken.
- Pregnancy test will be done; only those tested negative will be recruited into study.
- Blood (5 ml into clotted bottle) will be collected for hormonal assay (LH, oestradiol, progesterone). The serum hormonal levels will be used to estimate the cycle day at the time of presentation in relation to the day of ovulation based on the method described by Novikova et al (2007).

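### Does the secondary comparison of pregnancy rates need a baseline conception-probability covariate?

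*Combined protocol and SAP*

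**What the plan says.** Pregnancy rate is a secondary outcome (Section 7). For it, Section 9.1 states that Firth's "bias reduction method will be applied to compare the pregnancy rates between groups", with penalised profile likelihood intervals. No covariate is listed, so as written this is a two-group comparison. Section 4 allocates women "in 1:1 ratio according to a computer-generated randomisation list in blocks of 10 in sealed envelopes" and mentions no stratification factor.

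The plan does collect information on conception risk:

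- Section 5.1 admits women "requesting emergency contraception within 72 h of a single act of unprotected intercourse in the current menstrual cycle".
- Section 5.2 excludes those "uncertain about the date of the last menstrual period".
- Section 6.1 adds "A menstrual history will be taken" and "The serum hormonal levels will be used to estimate the cycle day at the time of presentation in relation to the day of ovulation".

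That information is used in two other places. The primary outcome in Section 7 relates observed pregnancies to the number expected under a published model. Section 9.1 also plans a split by ovulatory status: "The first subgroup analysis will stratify participants into pre-ovulatory versus post-ovulatory at the time of EC".

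**The concern.** Conception risk depends strongly on when in the cycle intercourse took place, and very few pregnancies will be observed. Without stratification, the arms can differ by chance in the number of women exposed near ovulation. The crude odds ratio then favours the lower-risk arm for reasons unrelated to piroxicam. A strong predictor is already on file, and leaving it out of the model looks like information thrown away. Silence on covariates could also seem to leave the choice of adjustment open until results are known. At stake would be a misleading secondary estimate in an imbalanced trial.

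**Working it through.** **Inputs.** From Section 9.2: 52% prevented on placebo, 62% on treatment, 80% power, type I error 0.05, 384 per group, 860 in total. From Section 2: a pregnancy rate of 2.15% (35/1625) on levonorgestrel. From Section 9.2: 51.9% prevented in the earlier levonorgestrel study. The spread of individual risk and the accuracy of the cycle-day estimate are not in the documents, so they are assumed and varied.

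**The plan's own figure.** Two-sided comparison of two proportions, pooled variance under the null:

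n = [1.96·√(2·0.57·0.43) + 0.8416·√(0.52·0.48 + 0.62·0.38)]² / 0.10² = (1.372 + 0.586)² / 0.01 ≈ 384.

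Allowing for 10% default, 384/0.9 = 427 per arm, or 854 in total, close to the stated 860. The check below uses 384 per arm.

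**Number of pregnancies.** Mean expected risk = 2.15% / (1 − 0.519) = 4.5%. The two figures come from different data sets, so this is approximate. Expected pregnancies per arm without treatment = 384 × 0.0447 ≈ 17.2. Observed: 17.2 × 0.48 ≈ 8.2 on placebo and 17.2 × 0.38 ≈ 6.5 on treatment, about 15 in all.

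**Assumed risk spreads.** A: 25% of women at 5–30%, the rest at 0.13%. B: 35% at 5–20%, the rest at 0.13%. C: 60% at 3–11%, the rest at 0.5%.

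**Size of the chance imbalance.** The SD of the between-arm difference in expected pregnancies is 13.6 / 10.6 / 6.0% of one arm's total (A / B / C). The RMSE of the crude log odds ratio with no effect is 0.519 / 0.515 / 0.521. The imbalance therefore accounts for roughly (0.136/0.519)² = 6.9%, (0.106/0.515)² = 4.2% and (0.060/0.521)² = 1.3% of its variability. The rest is the randomness of a small count, which no covariate removes.

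Trials at least 1 SD out of balance make up about 32%. For a normal variable, the mean absolute deviation in that group is 0.2420/0.1587 = 1.525 SD. This predicts a lean of 1.525 × 0.136 = 0.21, 1.525 × 0.106 = 0.16 and 1.525 × 0.060 = 0.09. The simulated values agree (first row of the table).

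**Effect of adding the term.** Firth penalised likelihood-ratio test, two-sided 0.05, one covariate (logit of conception probability). There were 8,000 trials per scenario with no effect, 4,000 at 62% and 3,000 at 90% prevented. The imperfect covariate has 30% of its values replaced by random draws.

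| A / B / C | Unadjusted | Imperfect covariate | Perfect covariate |
|---|---|---|---|
| Lean in imbalanced third, no effect | 0.22 / 0.16 / 0.09 | 0.12 / 0.09 / 0.04 | about 0 |
| RMSE in imbalanced third | 0.542 / 0.531 / 0.524 | 0.529 / 0.526 / 0.523 | – |
| RMSE, all trials | 0.519 / 0.515 / 0.521 | 0.527 / 0.522 / 0.523 | 0.538 / 0.528 / 0.525 |
| Type I error, % | 4.6 / 4.8 / 4.7 | 4.7 / 4.9 / 4.8 | – |
| Power, 52% vs 62%, % | 7.6 / 7.1 / 6.7 | – | 7.9 / 7.3 / 7.0 |
| Power, 52% vs 90%, % | 55.4 / 55.2 / 55.5 | 57.4 / 57.0 / 56.4 | – |

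With half the covariate values uninformative, the lean falls only to 0.17 / 0.13 / 0.06. The Monte Carlo SE is 0.24 points for type I error, 0.4 points for power near 7% and 0.9 points near 55%.

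**Second check with a different risk model.** Risk was bell-shaped over 28 cycle days (coefficient of variation 0.5 to 1.8), with no error or a 3-day SD error in cycle day, at 384 per arm and 4.5% mean risk:

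- Type I error was 4.1–5.1% without the term and 4.2–5.2% with it.
- Power at 52% versus 62% was about 6–7% either way.
- Power at 52% versus 80% was about 26–28% without and 27–30% with.
- RMSE was 0 to 5% larger with the term.
- In the most imbalanced fifth of trials, a 3-day error reduced the lean from 0.10–0.25 to 0.04–0.19.

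**Agreement with the primary outcome.** At 52% versus 62%, the crude comparison points the opposite way to the risk-scaled outcome in only 3.6 / 1.8 / 0.4% of trials. With the imperfect covariate this is 3.5 / 1.7 / 0.4%.

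**The case for a change.** The best case for adjusting concerns the reading of the one trial that will be run. If its arms turn out unbalanced, the crude odds ratio averages about 0.80 / 0.85 / 0.91 with no true effect (exp of −0.22 / −0.16 / −0.09), and a covariate roughly halves that lean on the log scale. The term needs no new data, and naming it in advance would fix the analysis.

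The lean and its partial removal are real, and both checks agree on them. They do not amount to a defect, for four reasons.

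- A lean of 0.2 to 0.4 of a standard error is small beside the noise of about 15 events. Even within the imbalanced third, RMSE improves by at most 2.4% (0.542 to 0.529), and by 0.2% in scenario C.
- Fixing the choice in advance gains little. Section 4 withholds the treatment codes from the investigators until the statistical analyses are done, and Section 9.1 describes only a two-group comparison. A choice made on coded groups remains conceivable, but nothing in the text invites it.
- The term has costs. It adds a parameter to a model with very few events, gives a conditional odds ratio with slightly more spread, and requires a probability table, a cycle-day rule and a floor for zero-risk days. A second odds ratio would also raise the question of which one carries the inference.
- A missing covariate would drop women, because "Cases with missing data in a certain parameter will not be analysed for that specific parameter; no data imputation will be instituted". A calendar rule would largely avoid this, but with cycles of 24 to 42 days admitted it may be imprecise, and its accuracy was not tested.

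**Conclusion.** The concern does not hold. It is true that no covariate and no stratification factor are named, but the unadjusted Firth comparison is a valid analysis of a secondary outcome. A plain pregnancy rate is a natural companion to a primary outcome that already divides by expected pregnancies. How far that division corrects imbalance in timing depends on the model giving each woman her own probability, which is inferred and not stated.

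Adding the term would leave type I error near 5% and power at the plan's own effect at about 6–8%. RMSE over all trials would be the same or up to 5% larger. The gain is partial removal of a 0.09 to 0.22 lean in about a third of trials. Reasonable statisticians would differ on that trade, and neither choice would change the trial's conclusions. The low power reflects the small number of pregnancies. It is a separate matter, which a covariate does not affect.

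The figures rest on a mean risk of 4.5% and on assumed risk spreads and cycle-day accuracy. The steepest profile tried (coefficient of variation 1.8) gave the largest changes, 2.6 points of power at 52% versus 80% and 5% in RMSE, and the conclusion was the same.
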